### **3.3 Benefit/Risk Assessment**

An overall risk/benefit assessment for each novel FRACTION-Gastric Cancer study treatment combination will be provided in each FRACTION-Gastric Cancer Sub-Protocol.

Non-live coronavirus disease 2019 (COVID-19) vaccination is considered a simple concomitant medication within the study. However, the efficacy and safety of non-live vaccines (including non-live COVID-19 vaccines) in participants receiving investigational agents is unknown.

#### **3.3.1 Safety Monitoring on Study Treatment**

Frequent safety assessments will be carried out by the Sponsor/BMS Medical Monitor (or designee) and investigators throughout the study to determine whether dose modification, additional safety measures, or termination of the study treatment combination arm is required at any time. In addition, AEs and serious adverse events (SAEs) will be reviewed regularly by the BMS Medical Monitor (or designee) and the Pharmacovigilance group to look for trends and potential safety signals. Treatment of AEs will follow institutional guidelines and recommended management algorithms, as listed in the Investigator's Brochure (IB) and prescribing information, as applicable, for each combination agent and control comparator, and provided as appendices to this protocol. Specific algorithms for the management of immune-related AEs are provided in [Appendix 6](#) and are applicable to immune-related AEs for all FRACTION-Gastric Cancer study treatment combinations.

## **4 OBJECTIVES AND ENDPOINTS**

The overall FRACTION-Gastric Cancer study-wide objectives are presented in the following sections. Any changes to these objectives for specific study treatments are specified in each FRACTION-Gastric Cancer Sub-Protocol.

**Table 4-1: Objectives and Endpoints**

Objectives	Endpoints

Primary
 
 
To assess the efficacy (ORR, DOR, and PFSR at 24 weeks) of each FRACTION-Gastric Cancer study treatment combination (relative to nivolumab in combination with ipilimumab, when applicable) in participants with advanced GC and/or EC
 
	
 
ORR, defined as the proportion of all treated participants with a BOR of CR or PR as assessed per RECIST v1.1 by investigator, median DOR, and PFSR at 24 weeks
 

Secondary
 
 
To investigate additional safety and tolerability of each FRACTION-Gastric Cancer study treatment combination in participants with advanced GC and/or EC
 
	
 
Incidence of AEs, SAEs, and AEs leading to discontinuation, deaths, and clinical laboratory test abnormalities
 

Tertiary/Exploratory
 
 
To assess the pharmacodynamic effects as a function of exposure, by evaluation of select biomarkers [REDACTED]
 
To explore potential associations between anti-tumor activity or safety and select biomarker measures [REDACTED]
 
To evaluate the PK of each IP component
 
To evaluate the immunogenicity of each IP, when applicable
 
To assess the OS in treated participants
 
To evaluate disease-related symptom improvement, as measured by the GaCS of the FACT-Ga and the ECS of the FACT-E in treated participants
 
To evaluate general health, functional status, and utility for health using the EQ-5D-3L in treated participants
 
	
 
Summary measures of change (or % change) from baseline or baseline level biomarker measurements [REDACTED]
 
Correlation (or similar appropriate measure of association) of biomarker measure [REDACTED]
 
Summary measures of PK parameters from serum concentration
 
Incidence of ADAs
 
OS rate at certain time points
 
Summary measures of EQ-5D-3L index and VAS scores, GaCS scores, and/or ECS scores, and corresponding change from baselines for each score
 

Abbreviations: CR = complete response; BOR = best overall response; DOR = duration of response; EQ-5D-3L = 3-level version of EQ-5D self-report questionnaire; EC = esophageal cancer; ECS = Esophagus Cancer Subscale; FACT-E = Functional Assessment of Cancer Therapy-Esophageal; FACT-Ga = Functional Assessment of Cancer Therapy-Gastric; GaCS = Gastric Cancer Subscale; GC = gastric cancer; IP = investigational product; RECIST = Response Evaluation Criteria in Solid Tumors; VAS = visual analog scale.

AEs and laboratory values will be graded according to NCI Common Terminology Criteria for Adverse Events (CTCAE) Version 4.03.

## 5 STUDY DESIGN

### 5.1 Overall Design

This is a rolling, Phase 2, adaptive study that will evaluate the preliminary efficacy, safety, tolerability, PK, and pharmacodynamics of novel FRACTION-Gastric Cancer study treatment combinations in participants with advanced GC and/or EC. The details pertaining to the specific study treatment regimens are provided in each FRACTION-Gastric Cancer Sub-Protocol.

Participants will be enrolled in 1 of the 2 tracks. Participants who are anti-PD-1, anti-PD-L1, and anti-CTLA-4 treatment naïve will be enrolled for Track 1. Participants who have had prior anti-PD-1, anti-PD-L1, or anti-CTLA-4 treatment will be assigned to Track 2, as outlined in [Figure 5.1-1](#) and described in [Section 5.1.1](#).

Participants on Tracks 1 and 2 will begin on the Treatment Phase (with a total duration of approximately 2 years). Tumor assessments will be conducted according to the timing described in each FRACTION-Gastric Cancer Sub-Protocol.

[figure not shown]
Participants in Tracks 1 and 2 will be treated until completion of the Treatment Phase, progression, toxicity, or protocol-specified discontinuation (see [Section 8.1](#)). The decision to continue treatment beyond investigator-assessed progression is possible (for up to completion of that Treatment Phase) and should be discussed with the BMS Medical Monitor (or designee) and documented in the study records (see [Section 7.4.2](#)). In addition, a participant with PD has the option to enter into Track 2, assuming that he/she continues to fulfill all eligibility criteria at each new randomization point, including a life expectancy of  $\geq 3$  months (see [Section 5.1.1](#)).

A Simon 2-stage (optimal) design will be used in both Tracks 1 and 2 to evaluate the possibility of terminating an arm early and/or moving promising combinations into the next phase of treatment development (see [Section 10.1](#)). The number of participants planned for enrollment may vary by track and is described in [Section 10.1](#). Enrollment will be continued after reaching the indicated number of participants at Stage 1 while the initial efficacy evaluation is ongoing. This will allow additional participants to enroll to account for unexpected trial impact, such as response nonevaluable participants due to early dropout, design parameter change (eg, historical rate update), etc. Participants who continue to fulfill eligibility criteria may move from Track 1 into Track 2 or re-enter Track 2, as described in [Section 5.1.1](#).

The study design schematic is presented in [Figure 5.1-1](#).

**Figure 5.1-1: Study Design Schematic**

Note: Participants treated with any study treatment targeting PD-1, PD-L1, or CTLA-4 will be considered anti-PD-1, anti-PD-L1, or anti-CTLA-4 treatment experienced, respectively.

Physical examinations, vital sign measurements, local 12-lead ECG, and clinical laboratory evaluations will be performed at selected times throughout treatment on all tracks (see [Section 2](#) and the On-treatment Procedural Outline[s] specific to each FRACTION-Gastric Cancer Sub-Protocol). Participants will be closely monitored for AEs and SAEs throughout the study. Blood and tumor tissue will be collected at specified times before and after study treatment administration for PK, ADA, and pharmacodynamic analyses. Participants may withdraw or discontinue at any time based on criteria in [Section 8.1](#).

### 5.1.1 FRACTION-Gastric Cancer Tracks 1 and 2 Design

A detailed study schematic for both Tracks 1 and 2 is presented in [Figure 5.1.1-1](#).

[figure not shown]
Participants who are naïve to anti-PD-1, anti-PD-L1, and anti-CTLA-4 treatment will be enrolled in Track 1, and they will be randomized to nivolumab in combination with ipilimumab or to one of the FRACTION-Gastric Cancer study treatment combinations. These participants will receive their assigned study treatment in Track 1 until completion of the Treatment Phase.

Participants who have received prior anti-PD-1, anti-PD-L1, or anti-CTLA-4 treatment will be enrolled in Track 2 and randomized to nivolumab in combination with ipilimumab, or to one of

the FRACTION-Gastric Cancer study treatment combinations. In addition, participants with PD who were treated in Track 1 or 2 and continue to fulfill all entry criteria may be enrolled in Track 2 and re-randomized to a new combination other than that previously received, if applicable. These participants will receive their assigned study treatment in Track 2 until completion of the Treatment Phase. The number of participants who initially enroll in Track 2 and those who enroll in Track 2 after treatment on Tracks 1 or 2 is described in [Section 10.1](#).

- **Participants with complete response (CR), PR, or SD** at the end of 2 years on Track 1 or 2 Treatment Phase will:
  - Enter safety follow-up and complete FU1, FU2, and FU3 visits
- **Participants with PD** during the Track 1 or 2 Treatment Phase will:
  - Enter safety follow-up and complete FU1, FU2, and FU3 visits
- **Participants with CR, PR, or SD who enter study follow-up and subsequently progress** will:
  - Enter safety follow-up and complete FU1, FU2, and FU3 visits

**Figure 5.1.1-1: Tracks 1 and 2 Study Design Schematic**

Note: This diagram presents the protocol-mandated treatment flow for Tracks 1 and 2, including re-entry into Track 2.

a Participants naïve to anti-PD-1, anti-PD-L1, and anti-CTLA-4 treatment will be enrolled in Track 1; participants with prior exposure to anti-PD-1, anti-PD-L1, and anti-CTLA-4 treatment will be enrolled in Track 2. Following track assignment, participants will be randomized.

b CR, PR, SD, and PD, as defined by RECIST v1.1. Assessments of PR and CR must be confirmed at least 4 weeks later following initial assessment.

c Safety Follow-up Phase.

d Not applicable as of Protocol Amendment 06: If participants are eligible and if a new study treatment combination is available, they can enroll/re-randomize to a new combination.

e Not applicable as of Protocol Amendment 06: Each individual participant may receive multiple study treatments, including initial treatment, treatment beyond investigator-assessed progression, and/or entry into Track 2, assuming that the participant continues to fulfill all eligibility criteria at each new randomization point (see Section 5.1.3.2 for details).

f Not applicable as of Protocol Amendment 06: Participants with PD during treatment may continue treatment beyond progression up to 2 years if criteria in Section 7.4.2 are met.

Abbreviations: CR = complete response; RECIST = Response Evaluation Criteria in Solid Tumors.

### **5.1.2 Safety Monitoring Board and Other External Committees**

Two independent committees may be utilized: a Safety Monitoring Board (SMB) and an Independent Review Committee (IRC).

The SMB will be established to provide safety monitoring and to provide advice to the Sponsor regarding actions the committee deems necessary for the continuing protection of participants enrolled in the study. The SMB will meet at least twice per year concurrent with BMS internal continuous safety assessments. If needed, additional ad hoc SMB meetings may be convened. Safety-related data summaries and listings (by study track and study treatment arm, as appropriate) will be provided to SMB to facilitate safety monitoring. The SMB will act in an advisory capacity to BMS and will monitor participant safety throughout the study. Additional details are provided in the SMB Charter.

The IRC may be established at the discretion of the Sponsor. The IRC may review all available tumor assessment scans to determine response (Response Evaluation Criteria in Solid Tumors [RECIST] v1.1 criteria). IRC-determined response may be used in the analyses of ORR, PFSR, and duration of response (DOR).

### **5.1.3 Study Phases**

Participants will complete up to 3 phases of the study: Screening, Treatment, and Safety Follow-up.

#### **5.1.3.1 Screening**

Prior to screening for the protocol, investigative sites are required to determine if a participant has previously received anti-PD-1, anti-PD-L1, or anti-CTLA-4 treatment through their institutional database, participant medical history, or institutional prescreening process. Once determined, treatment experience is considered source data for this FRACTION-Gastric Cancer study. The participant must be provided with the FRACTION-Gastric Cancer study Institutional Review Board (IRB)-approved written consent. Once the consent is signed, the participant is then considered to have entered screening. The treatment status must be entered into the enrollment management system, and participants will be required to submit a fresh tumor biopsy. An adequate baseline tumor biopsy (as determined by a central laboratory pathologist) must be obtained prior to randomization.

The Screening Phase for each track will last for up to 28 days. Participants will be enrolled using Interactive Response Technology (IRT).

If a participant surpasses the 28-day window during the Screening Phase due to a study-related procedure (eg, scheduling of a tumor biopsy or waiting time for a study-related laboratory value), the participant must be re-consented but does not need to be assigned a new participant identification number. To reduce any undue burden of procedure in this participant population in this situation, the amount of repeat procedures from the initial screening will be minimized, while maintaining safety and eligibility under the discretion of the BMS Medical Monitor (or designee) and investigator.

Enrollment in all study treatment arms in each track will be competitive.

### **5.1.3.2 Treatment**

The details of the Treatment Phase duration are provided in [Section 5.1](#). Further details of the study treatment administration are in each FRACTION-Gastric Cancer Sub-Protocol. Study assessments are to be collected as outlined in the On-treatment Procedural Outline(s) in each FRACTION-Gastric Cancer Sub-Protocol.

Assessment of response will be outlined for each combination therapy in the specific FRACTION-Gastric Cancer Sub-Protocol. Assessments of PR and CR must be confirmed at least 4 weeks later following initial assessment. Tumor progression or response endpoints will be assessed using RECIST v1.1 criteria for solid tumors (see [Appendix 5](#)).

Participants will generally be allowed to continue study treatment until the first occurrence of one of the following: 1) completion of 2 years of study treatment, 2) PD, 3) clinical deterioration suggesting that no further benefit from study treatment is likely, 4) intolerable toxicity, and 5) meeting of criteria for discontinuation of study treatment, as outlined in [Section 8.1](#). Individual participants with confirmed CR will be given the option to discontinue study treatment, on a case-by-case basis, after specific consultation and agreement between the investigator and the BMS Medical Monitor (or designee) in settings where the benefit/risk ratio justifies discontinuation of study treatment.

All participants will be treated as per [Section 5.1](#), unless criteria for study treatment discontinuation are met earlier (see [Section 8.1](#) in this FRACTION-Gastric Master Protocol and [Section 8.1](#) in the FRACTION-Gastric Cancer Sub-Protocol). Upon completion of the Treatment Phase, all participants will enter the Safety Follow-up Phase (see [Section 5.1.3.3](#) and [Table 2-3](#)).

As of Protocol Amendment 06, collection of blood or other biological samples for reasons other than safety monitoring (eg, PK, ADA, biomarkers, etc) should be discontinued. Please refer to [Table 2-3](#) and [Sections 9.5, 9.6, and 9.8](#).

### **5.1.3.3 Follow-up**

As of Protocol Amendment 06, tumor scans, survival status follow-ups, and collection of subsequent treatment information will end once the participant has disease progression or treatment discontinuation for any reason, whichever occurs first. Any assessments for monitoring of safety will continue per protocol until the final follow-up visit (FU3). Please refer to [Table 2-3](#).

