**Table 2-3: Follow-up Procedural Outline**

Procedure	Safety Follow-up a			Notes
	FU 1 30 Days (± 7 Days)	FU 2 60 Days (± 7 Days)	FU 3 100 Days (± 7 Days)	
Patient-reported Outcomes Assessment c	X	X	X	EQ-5D-3L and GaCS and/or ECS Can be collected by telephone at regularly scheduled times
Collection of Survival Status and Subsequent Treatment Information c	X	X	X	Safety follow-up visits must occur in the office. Response (and survival) follow-up visits may be performed by telephone contact or clinic visit.

a FU visits at 30, 60, and 100 days (± 7 days) should occur after the last dose of study treatment or coinciding with the date of discontinuation ± 7 days, if the date of discontinuation is greater than 30 days after the last dose, to monitor for AEs.

b Not applicable as of Protocol Amendment 06: Additional survival follow-up will be collected every 6 months for 3 additional years (2 years of response follow-up + 3 years of survival follow-up = total of 5 years of follow-up). BMS may request that survival data be collected on all treated/randomized participants outside of the protocol-defined window. At the time of this request, each participant will be contacted to determine their survival status unless the participant has withdrawn consent for all contacts or is lost to follow-up. Withdrawal of consent must be clearly documented. See [Section 5.1.3.3](#) for details.

c As of Protocol Amendment 06: Assessments necessary for monitoring safety (eg, safety labs, oxygen saturation, vital signs, physical exams, review of concomitant medications, AE/SAE reporting, etc) will continue per sub-protocol until the FU 3 visit. Tumor Scans, survival status follow-ups, and collection of subsequent treatment information will end once the participant has disease progression, or treatment discontinuation for any reason, whichever occurs first. Collection of samples for PK, ADA, biomarkers, as well as collection of data for patient-reported outcomes should be discontinued. The intent is to minimize the burden on study participants and site staff.

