### 10.3 Statistical Analyses

The statistical analysis plan will be developed and finalized before database lock. Below is a summary of planned statistical analyses of the primary and secondary endpoints.

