#### 10.3.1 Efficacy Analyses

The primary efficacy analyses will be performed on treated population for the final analysis. Efficacy analyses based on the response-evaluable population may be performed for interim analyses, when the minimum follow-up period is less than sufficient to warrant adequate interpretation of the result. Details on censoring scheme on time-to-event endpoints such as DOR, PFS, and OS will be described in the SAP.

Endpoint	Statistical Analysis Methods
ORR BOR for a participant will be assessed per RECIST v1.1 by investigator.	Estimate of ORR and corresponding 2-sided exact 95% CI will be derived using the Clopper-Pearson method by study treatment under each track.
Median DOR DOR for a participant with a BOR of CR or PR is defined as the time between the date of first response and the date of the first objectively documented tumor progression per RECIST v1.1 or death, whichever occurs first.	Median DOR using the Kaplan-Meier method and corresponding 2-sided 95% CI will be derived using Brookmeyer and Crowley methodology (using log-log transformation) by study treatment under each track.
PFSR at 24 weeks PFS for a participant is defined as the time from the first dosing date to the date of first objectively documented disease progression or death due to any cause, whichever occurs first.	Estimate by the Kaplan-Meier method and corresponding 95% CI will be derived based on Greenwood formula by study treatment under each track.
OS rate at certain time points OS for a participant is defined as the time from the first dosing date to the date of death due to any cause.	Estimate by the Kaplan-Meier method and corresponding 95% CI will be derived based on Greenwood formula by study treatment under each track.

Treatments under each track for different populations will be analyzed independently. There is no intention to combine the same study treatment across tracks for efficacy analyses.

Efficacy from retreatment will be assessed and analyzed separately from the initial treatment.

Participants re-randomized into Track 2 will be combined with participants originally randomized into Track 2 for efficacy analysis.

Specific analyses to be performed for each track are shown in [Table 10.3.1-1](#).

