**Track 1 - Anti-PD-1, Anti-PD-L1, and Anti-CTLA-4 Treatment-naïve Participants**

The following additional analyses will be performed for Track 1 anti-PD-1, anti-PD-L1, and anti-CTLA-4 treatment-naïve participants combined at end of Stage 2. These efficacy analyses will be performed when the study treatment arms have been fully enrolled and followed up for at least 6 months. A descriptive odds ratio and estimate of the difference in ORRs, along with corresponding 2-sided 95% CIs, will be provided to evaluate differences between the 2 randomized study treatment arms (FRACTION-Gastric Cancer study treatment combination arm and nivolumab in combination with ipilimumab control arm). Additionally, for each study treatment arm, the ORR and corresponding 95% CIs will be calculated using Clopper-Pearson method. A descriptive hazard ratio and corresponding 2-sided 95% CI of PFS and OS will be estimated in a Cox proportional hazards model using study treatment as a single covariate to evaluate difference between the 2 study treatment arms (experimental and control arms). The PFS and OS curves for each study treatment arm will be estimated. Two-sided 95% CIs for median PFS and OS will be computed. PFSR at 24 weeks and survival rates at certain time points (eg, 2 years) will be estimated. Associated 2-sided 95% CIs will be calculated.

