## **COMPLIANCE WITH THE PROTOCOL AND PROTOCOL REVISIONS**

The investigator should not implement any deviation or change to the protocol without prior review and documented approval/favorable opinion of an amendment from the IRB/IEC (and if applicable, also by local health authority) except where necessary to eliminate an immediate hazard(s) to study subjects/participants.

If a deviation or change to a protocol is implemented to eliminate an immediate hazard(s) prior to obtaining relevant approval/favorable opinion(s) the deviation or change will be submitted, as soon as possible to:

- IRB/IEC
- Regulatory Authority(ies), if applicable by local regulations (per national requirements)

Documentation of approval/favorable opinion signed by the chairperson or designee of the IRB(s)/IEC(s) and if applicable, also by local health authority must be sent to BMS.

If an amendment substantially alters the study design or increases the potential risk to the participant: (1) the consent form must be revised and submitted to the IRB(s)/IEC(s) for review and approval/favorable opinion; (2) the revised form must be used to obtain consent from subjects/participants currently enrolled in the study if they are affected by the amendment; and (3) the new form must be used to obtain consent from new subjects/participants prior to enrollment.

If the revision is done via an administrative letter, investigators must inform their IRB(s)/IEC(s).

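### Amendment 06 ends survival follow-up at progression or treatment stop, but Section 10.3.1 still plans OS rates and an OS hazard ratio, so OS censoring is informative for participants on treatment at the amendment

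*Combined protocol and SAP*

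**What the plan says.** **Follow-up.** Section 5.1.3.3 states that "tumor scans, survival status follow-ups, and collection of subsequent treatment information will end once the participant has disease progression or treatment discontinuation"; the earlier of the two events applies. Footnote c of Table 2-3 repeats that this collection "will end once the participant has disease progression, or treatment discontinuation for any reason, whichever occurs first". Safety assessments continue to the third follow-up visit. Section 5.1.3.3 (Safety Follow-up) keeps SAE collection to 100 days after dosing stops, and Appendix 3 counts death as an SAE outcome, so deaths in that window are still recorded.

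**Analysis.** Section 10.3.1 defines OS from first dose to death from any cause and plans Kaplan-Meier OS rates by treatment within each track. Table 10.3.1-1 marks OS for both tracks. For Track 1 at the end of Stage 2, once arms are fully enrolled and followed at least 6 months, the section adds: "PFSR at 24 weeks and survival rates at certain time points (eg, 2 years) will be estimated". It also says: "A descriptive hazard ratio and corresponding 2-sided 95% CI of PFS and OS will be estimated in a Cox proportional hazards model".

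**Censoring and cut.** Section 10.3.1 says: "Details on censoring scheme on time-to-event endpoints such as DOR, PFS, and OS will be described in the SAP". Section 10.3 says: "The statistical analysis plan will be developed and finalized before database lock". Section 10.3.4 ties database lock to completed treatment and sufficient follow-up, not to the amendment. The amendment's list of changes has no Section 10 entry.

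**Status of OS.** Table 4-1 lists "To assess the OS in treated participants" under tertiary/exploratory objectives.

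**The concern.** Kaplan-Meier and Cox estimates assume that a participant censored at a given time has the same outlook as those still followed. The amendment splits the sample in two.

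- **Already off treatment at the amendment.** Survival follow-up stops on a calendar date unrelated to the participant's condition. This is ordinary administrative censoring.
- **Still on treatment at the amendment.** Survival follow-up now stops because the participant progressed or came off treatment, and both predict death. The high-risk time after progression is under-represented, so estimated OS is too high.

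The 100-day SAE window softens this but does not remove it. No section says whether deaths found there count in OS, or whether survivors are censored at Day 100 or at the last survival contact, and that choice changes the size of the bias. What is at stake is how the OS rates are read, above all a 2-year rate.

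**Working it through.** The plan states no OS event count, power or expected rate, so there is no OS figure of its own to reproduce. The check is an illustration of size.

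**Inputs from the protocol (Section 3.2.1).** 12-month PFS rate 17%; median OS 8 to 14 months. Using these two sources together is an assumption.

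**Other assumptions.** Constant hazards. Share q of PFS events that are deaths: 0.1, 0.2 or 0.3. Uniform entry. Scenarios are written as entry period/amendment time in months from first entry. Progression stands for the end of treatment. The model omits stops without progression and the 2-year treatment cap, and censors anyone already progressed at the amendment on that date.

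**Formulas.**
- PFS hazard: λ = −ln(0.17)/12 = 0.148 per month.
- True OS: S(t) = e^(−λt) + λ(1−q)[e^(−μt) − e^(−λt)]/(λ−μ), with the post-progression hazard μ solved so that S(median) = 0.5.
- Share event-free at the amendment:
  - 24/24: (1 − e^(−24λ))/(24λ) = (1 − 0.029)/3.544 = 27%.
  - 36/36: (1 − 0.005)/5.316 = 19%.
  - 36/48: (0.17 − 0.17⁴)/5.316 = 3%.

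**Main reading:** Day-100 deaths counted, survivors censored at Day 100. Each scenario simulates 400,000 participants; Monte Carlo error is about 0.2 points at 12 months. Rows for q = 0.1, OS in % at 12/24 months:

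| Scenario | Median OS | True | Full data | Bias | Cut at amendment |
|---|---|---|---|---|---|
| 24/24 | 8 | 29.8/5.5 | 33.4/10.1 | +3.6/+4.6 | 29.8/5.1 |
| 24/24 | 11 | 45.6/13.2 | 49.1/20.8 | +3.5/+7.6 | 45.8/13.3 |
| 24/24 | 14 | 57.1/24.0 | 59.6/31.2 | +2.5/+7.2 | 57.1/24.2 |
| 36/36 | 8 | 29.8/5.5 | 32.1/8.0 | +2.3/+2.5 | 29.8/5.4 |
| 36/36 | 11 | 45.6/13.2 | 47.9/16.6 | +2.3/+3.4 | 45.9/13.2 |
| 36/36 | 14 | 57.1/24.0 | 58.6/27.0 | +1.5/+3.0 | 57.0/24.0 |

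Bias falls as q rises; at q = 0.3 the 24/24 bias at 12 months can be as low as about +0.4.

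**Longer accrual, all q (12-month; 24-month bias, points).**
- 36/48: about 0; +0.1 to +0.7.
- 48/48: +0.1 to +1.7; +0.4 to +2.2.
- 60/60: +0.2 to +1.4; +0.3 to +1.6.
- 48/60: about 0; +0.1 to +0.4.

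**Other handling of Day-100 deaths (24/24, 12 months).** Later deaths not counted: +0.6 to +7.4. Deaths counted but survivors censored at progression: −0.8 to +2.5.

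**Numbers at risk at 24 months under a cut, 54-participant arm.** 54 × S(24) × share entered at least 24 months earlier; for example 36/36, median OS 11: 54 × 0.132 × 12/36 = 2.4. Across the model: below 0.1 (24/24, read at 23.9 months), 1 to 5 (36/36), 2 to 11 (36/48).

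**OS hazard ratio, full data relative to the cut.** 0.94 to 1.00 if the PFS hazard ratio is 0.6; 0.98 to 1.00 if 0.8; 1.00 if 1.0.

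**PFSR at 24 weeks.** With 5 to 20% assumed to stop without progression before Week 24 and the later hazard halved or doubled, the effect is −0.4 to +0.5 points (24/24), −0.3 to +0.3 (36/36) and 0 (36/48).

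**The case against.** **The rule is deferred, not shown to be absent.** Censoring is sent to an SAP that may be finalized up to database lock, and Section 10.3 describes itself as a summary for primary and secondary endpoints, while OS is exploratory. This stands: a reader might infer that the sponsor has no OS censoring rule, and the documents cannot show that. What they show is a follow-up rule and an OS analysis that do not fit together, with no cut stated.

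**The Track 1 analysis may never run.** The hazard ratio and the 2-year example depend on full enrolment and at least 6 months of follow-up, which early closure may prevent, and 2 years is only an example. This stands. The OS rates by treatment in both tracks carry no such condition.

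**The largest figures come from short accrual.** The 24/24 scenario puts every entry after about August 2019. The document history dates the original protocol 12-Aug-2016 and Amendment 06 13-Aug-2021, 60 months apart. The rationale for Revised Protocol 04 (03-May-2019) already reports inconsistent biopsy quality, which suggests earlier entries. This stands: the upper ends are limits, not expectations. It also means that a 2-year OS rate cannot be called unsupportable outright; that follows only if entry ran about 24 months up to the amendment.

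**A cut costs precision.** With 54 participants, the 12-month root mean squared error is higher under the cut: 7.9 to 8.4 against 7.2 to 7.9 points (24/24) and 7.1 to 7.7 against 6.9 to 7.4 (36/36); for 36/48 the two are equal. This stands. A reader might infer that the cut should replace the full-data analysis; these figures do not support that.

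**Burden.** Footnote c aims to spare participants and sites. This is a reason to use vital status already in site records rather than new contacts.

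**Conclusion.** The point holds as a minor one. The amended follow-up rule makes OS censoring depend on prognosis for participants on treatment at the amendment, and the statistical section neither acknowledges this nor sets a cut. With Day-100 deaths counted, OS is overstated by about 0 to 3.6 points at 12 months and about 0 to 7.6 points at 24 months. The size depends mainly on the share on treatment at the amendment, which the documents do not give; with few such participants the bias is close to zero. All figures rest on the assumed accrual, constant hazards and the pairing of the two Section 3.2.1 sources.

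Two stronger readings are not supported. One is that OS is distorted for the whole sample: those already off treatment are censored administratively. The other is that the go/no-go decisions are compromised: the Simon boundaries use ORR, OS is exploratory, the hazard ratio is descriptive, and the estimated PFSR effect is within about 0.5 points.

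**What to change.** In Section 10.3.1 and the SAP:

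1. State whether deaths found in the 100-day safety window count in OS, and where Day-100 survivors are censored.
2. Beside the full-data OS analysis, report a sensitivity analysis with one administrative cutoff for all participants, no later than the earliest site implementation of Amendment 06, using vital status as of that date already in site records and not counting later deaths. Site dates can differ because Appendix 2 bars a change "without prior review and documented approval/favorable opinion of an amendment from the IRB/IEC". With sites implementing over 3 or 6 months (24/24), a cut at the latest date leaves +0.2 to +1.1 or +0.1 to +1.4 points of bias at 12 months, against within about 0.2 at the earliest.
3. Show numbers at risk and drop OS landmarks, such as 2 years, that follow-up does not support.

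Repeating PFSR and DOR under the same cut is optional.

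**Cost.** Wording, one cut rule and one check of existing records; no new participants, visits or scans. The cut analysis has fewer OS events: 18 to 23% fewer (24/24), 10 to 15% (36/36), 1 to 2% (36/48), and 22 to 28% (24/24) if sites implement over 3 to 6 months and the earliest date is used. The 95% CI half-width for 12-month OS with 54 participants goes from 13–14.5 to 15–16 points (24/24), from 13–14 to 14–15 (36/36), and is unchanged (36/48). The record check matters: without it, and with contacts up to 6 months apart, the cut analysis is itself off by −2.1 to +1.8 points (24/24) or −0.4 to +0.3 (36/48). For these reasons it belongs beside the full-data analysis, not in its place.
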